# **Data Collection Methods/Assessment and Schedules**

Data will be collected by the PI and the co-investigators. Hospital charts will be reviewed for pertinent clinical information. Results of liver biopsies and blood chemistries will be obtained from the Cerner Power Chart computer system. Specifically, the history of present illness, past medical history, and birth history, pertinent physical exam findings including patient weight, the results of liver biopsies, and parenteral and enteral feeding history will be collected. The information will be recorded on hard copy data collection forms.

# **Study Protocol Timeline**

This study protocol will end five years following commencement of the study.

# **Adverse Event Criteria and Reporting Procedures**

Adverse events (AEs) will be assessed from the time of the first Omegaven® infusion until exit from the study. In particular, the patient will be observed during and shortly

after Omegaven® administration for the occurrence of anaphylactic or allergic reactions. Patients experiencing any adverse events that are moderate or severe in nature and that may be related to Omegaven® will have their treatment temporarily halted until the adverse event has resolved. Dose modifications in the event of hypertriglyceridemia, hyperglycemia and coagulopathy will occur as described above. Should patients be dose reduced for adverse events that are later considered to be unrelated to the study medication, treatment will recommence at the dose they had received prior to the dose reduction. Patients with anaphylactic or allergic reactions will not continue Omegaven® treatment.

Any serious or unsuspected adverse events will be reported to the Institutional Review Board and to the FDA within 72 hours of the occurrence, or immediately if the event is fatal or life threatening as per CHS IRB Policy on Adverse and Unexpected Events and Unanticipated Risks to Research Subjects and Others. This will be done in person or by telephone, and by completion of the IRB form for adverse/unexpected event reporting.

Unanticipated adverse events will be detected by the monitoring of vital signs, physical exams and laboratory analysis for all participants, as well as by observation by the nursing staff and guardians (following instruction) if participant is an outpatient. Events will be reported to the investigators immediately by telephone or pager, and subsequently to the appropriate board or committee.

The IRB will be responsible for assuring that adverse event reporting requirements are met. Any patients who have agreed to participate in the study protocol, but who have not yet undergone intervention, will be informed of the adverse event.

All AEs will be assessed by the Investigator and recorded in a case report form, inclusive of the date of onset and resolution; severity; relationship to study medication; outcome and action taken with the study medication. In addition, the clinical severity of all AEs will be recorded and graded using the standard definitions of mild, moderate, severe or potentially life threatening with serious adverse events (SAE) deemed to be those severe to potentially life threatening (Table 3). Once an AE or SAE is identified, research team members will ensure that the participants receive appropriate care and that all actions taken by the PI after observing the AE or SAE are documented. In addition, all AE or SAEs will be classified and documented by the Investigator as definitely, probably, possibly, or probably unrelated to administration of study drug.

Patients will be withdrawn from the study for any of the following:

- a) Toxicity considered unacceptable by the Investigator note: no adverse effects have been observed in patients receiving Omegaven® that could be attributed to its use
- b) Patient/guardian requests to discontinue treatment and/or observation for any reason
- c) A suitable organ has been located and the patient is able to undergo a liver or liver/intestinal transplant
- d) Decision by the Investigator that termination is in the patient's best medical interest

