#### Inclusion Criteria:

- 1. Children 0-18 years of age
- 2. Patients will be PN-dependent and expected to continue PN for at least 30 days
- 3. Patients considered eligible for study participation must have PN-associated liver diseases. Other causes of liver disease (i.e., biliary atresia, galactosemia, alpha-1 antitrypsin deficiency) will be excluded. A liver biopsy is not necessary for treatment
- 4. Direct bilirubin > 2.0 mg/dl
- 5. Signed patient informed consent
- 6. Signed patient assent where applicable.

The patient will be hospitalized at the time of enrollment and initiation of Omegaven®.

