# Hyperglycemia:

If hyperglycemia develops, defined as serum glucose levels >250mg/dL, other sources of hyperglycemia should be considered and addressed (sepsis). A minimum dosage reduction of 25% will occur. Blood sugars will continue to be monitored closely with additional adjustments as warranted.

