# **Definition of Primary and Secondary Outcomes/Endpoints**

The primary outcome is normalization of direct bilirubin to less than 0.4mg/dL by 9 months.

Seconday outcomes include:

- Omegaven® will prevent EFA deficiency as evidenced by normal EFA profiles on monthly evaluations
- The rate of triglyceride levels > 400 mg/dL with Omegaven® will be similar to that seen with PN administered with soy oil IFE (conventional emulsion, i.e., Intralipid®) as evidenced by baseline data and then weekly and monthly evaluations
- PN containing Omegaven® will be safe for patients with respect to the risk of unexpected bleeding/coagulopathies as evidenced by weekly and monthly evaluations

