# Omegaven® Possible Adverse Events

CLINICAL							
GRADE I	GRADE II	GRADE III - SAE	GRADE IV - SAE				
(MILD)	(MODERATE)	(SEVERE)	(POTENTIALLY				
, , ,	, , , , , , , , , , , , , , , , , , ,	,	LIFE				
			THREATENING/				
			DEATH)				
Phlebitis	Hypotension	Bowel obstruction	Uncontrolled				
			bleeding				
Fever	Hypertension	Sepsis syndrome	Anaphylaxis				
Fishy taste	Urinary tract		Shock				
	infection						
Chills	Poor growth		Death				
Flushing	Priapism						
Cyanosis							
Nausea/Vomiting							
Dehydration							
Rash							
LABORATORY							
Hyperglycemia	Anemia	Sepsis	Coagulopathy				
Hypertriglyceridemia	Leukopenia						
Essential fatty acid	Thrombocytopenia						
deficiency	_						
Electrolyte	Abnormal liver						
abnormalities	function tests						
	Positive urine						
	culture

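### SAEs are defined by severity and tied to a table that fixes each event name at one grade, so some serious events could miss the 72-hour report

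*Protocol*

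**What the plan says.** Under Adverse Event Criteria and Reporting Procedures, the protocol requires that "the clinical severity of all AEs will be recorded and graded using the standard definitions of mild, moderate, severe or potentially life threatening". It names no scale. The same sentence continues with the definition of seriousness: "serious adverse events (SAE) deemed to be those severe to potentially life threatening (Table 3".

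The table meant is the last one in the protocol, on possible adverse events with Omegaven. (The laboratory schedule also carries the number 3, but the text calls that one Table 2.) It has four grade columns, and the headings of Grades III and IV carry the label SAE. Each event name stands in one column. In the laboratory part, "Hyperglycemia" and "Hypertriglyceridemia" are Grade I, as are electrolyte abnormalities. Thrombocytopenia and abnormal liver function tests are Grade II. "Coagulopathy" is Grade IV. No entry has a cut-off.

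The adverse event section also sets what follows from SAE status. Serious or unsuspected events go to the IRB and FDA within 72 hours, and fatal or life-threatening ones go immediately, under the institution's IRB policy.

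**The concern.** Severity and seriousness are different things. Severity describes how intense an event is. Seriousness describes its outcome: death, threat to life, hospitalization or its prolongation, lasting disability. Expedited reporting exists for the second. This protocol uses the first as the test, then points to a table that cannot measure it, because each name has one grade whatever the value or the clinical picture.

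Expedited reporting is what is at stake. A severe but expected metabolic or haematologic event, or a moderate event that keeps a child in hospital, could be left out of the 72-hour report. Investigators who take the table literally and those who grade by what they observe could also record different SAEs for the same child, in an open-label study whose purpose includes safety.

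**Working it through.** The protocol gives no event rates or grade thresholds, so there is no figure to reproduce. The check is a count of the table and a comparison of readings.

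**Count of table entries** (nausea/vomiting taken as one term)

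| Part | Grade I | Grade II | Grade III (SAE) | Grade IV (SAE) | Total |
|---|---|---|---|---|---|
| Clinical | 9 | 5 | 2 | 4 | 20 |
| Laboratory | 4 | 5 | 1 | 1 | 11 |
| Total | 13 | 10 | 3 | 5 | 31 |

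At SAE grades: 3 + 5 = 8. Not at SAE grades: 13 + 10 = 23. Of the 11 laboratory terms, 2 (sepsis and coagulopathy) carry the SAE label and 9 do not.

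**The same event under two readings of the rule**

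| Event | Grade by observed severity | Grade by table name |
|---|---|---|
| Severe hyperglycemia, hypertriglyceridemia or electrolyte abnormality | Severe, so SAE | Grade I, not SAE |
| Severe thrombocytopenia or liver test abnormality | Severe, so SAE | Grade II, not SAE |
| Coagulopathy of less than severe degree | Not SAE | Grade IV, SAE |
| Moderate urinary tract infection that prolongs the stay | Moderate, not SAE | Grade II, not SAE |
| Death, shock, anaphylaxis, uncontrolled bleeding | SAE | SAE |

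The first three rows differ between the readings, in both directions. The fourth row gives the same answer on both, and that answer comes from using severity as the test. It is a realistic case, because the inclusion criteria state: "The patient will be hospitalized at the time of enrollment and initiation of Omegaven".

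**Thresholds elsewhere in the protocol.** They exist, but they do not set grades. For glucose above 250 mg/dL, the Hyperglycemia section says "A minimum dosage reduction of 25% will occur". Triglycerides above 200 mg/dL bring in the dose modification steps, and a secondary outcome concerns a higher level: "The rate of triglyceride levels > 400 mg/dL with Omegaven® will be similar". Coagulopathy has a dose rule but no laboratory threshold.

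**Route to a missed report.** An event labelled Grade I or II is not an SAE under the literal reading. It still goes to the IRB and FDA if it is unsuspected, fatal or life threatening. What remains is the event that is expected, severe and not life threatening. On either reading, the expected moderate event that prolongs hospitalization also remains.

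**The case against.** The strongest reply is that there is one rule, not two. Investigators grade observed severity, severe or worse is an SAE, and the table is an illustrative list of possible events. The title fits that reading, and under it the first three rows of the comparison cease to conflict. This is plausible, but the protocol does not say it. The definition of SAE cites the table, and the table prints SAE in its column headings. The fourth row is untouched.

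The table also allows some escalation by name: hypotension to shock, urinary tract infection to sepsis, rash to anaphylaxis. That stands, and it confines the literal-reading problem mainly to the metabolic, haematology and liver test entries.

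Third, care does not hang on the grade in the main examples. Triglycerides, glucose and coagulopathy have their own dose rules, and no listed outcome uses SAE counts or grades. A dose threshold need not be a grade threshold either, so their absence from the table is not in itself a contradiction. This stands and limits the harm to reporting.

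Fourth, the IRB policy, Good Clinical Practice and FDA guidelines that the protocol cites may define seriousness by outcome and catch these events. They are not reproduced in the protocol, so this can be neither confirmed nor ruled out. The protocol nevertheless states a rule of its own.

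Two stronger inferences should be resisted. A reader might conclude that a related laboratory coagulopathy, being Grade IV, would halt the study. The Data and Safety Monitoring Plan halts for a life-threatening episode related to Omegaven and refers neither to the table nor to Grade IV, whose heading says potentially life threatening. A reader might also conclude that any small change in a clotting test becomes an SAE. The table says coagulopathy, not an abnormal PT or INR, and the dose section treats it as reason to reduce or stop the drug. An error there would in any case be towards over-reporting.

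**Conclusion.** The point holds as a defect in the SAE definition, of minor to moderate weight. Using severity as the test for seriousness leaves out moderate events that prolong hospitalization, and this does not depend on how the table is read. The further loss of severe metabolic, haematologic and liver test events depends on applying the table literally, which the wording permits but does not compel. Both conclusions assume that the adverse event section is followed as written and is not overridden by the cited policies.

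The documents do not support a claim that such events will go unreported, only that they could. With 20-25 children planned and no event rates given, the number affected cannot be estimated; 8 of 31 terms at SAE grades describes the table, not the consequences.

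**What to change.** In Adverse Event Criteria and Reporting Procedures:

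- Define an SAE by outcome: death, threat to life, hospitalization or its prolongation, or lasting disability. State that this is judged separately from the severity grade.
- Name the severity scale, with its version, in place of the unnamed standard definitions.
- State, there and in a note to the adverse event table, that the entries are examples and that grade follows observed severity. Remove the SAE label from the Grade III and IV headings, so that grade no longer implies seriousness.

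The halting rule in the Data and Safety Monitoring Plan needs no change.

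The cost is wording. Glucose, triglycerides, electrolytes, platelets, liver tests and coagulation tests are already on the laboratory schedule. The downside is a few more events to report, chiefly those that prolong hospitalization.

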## e) Patient is lost to follow-up.

In the event that a patient is withdrawn, the Investigator will document the date of withdrawal, the reason for withdrawal, and the results of all assessments made up to the date of withdrawal.

# **DATA MANAGEMENT AND STATISTICAL ANALYLSIS**

# **Data Management Methods**

Overview

This phase II clinical trial study will be supported by an Access-based data management system (DMS). The system will include a protocol management system that assists study staff with accurate collection of study data and monitors protocol adherence. The system will provide and be linked to a data entry system. Features of the system include double data entry, data range and logic checks, cross form validations at the time of data entry and audit trails of entered and corrected data.

Protocol Management and Protocol Status

All study related tasks will follow Good Clinical Practice Guidelines. Protocol status reports from the protocol management system will allow the principal investigator to monitor protocol adherence on a regular basis.

Data Entry and Databases

Study results will be entered into the DMS from paper based case report forms that will be completed by the investigators.

Confidentiality, Security, Back-Up

The databases will be located on the CHS Network and therefore backed - up on a daily basis. All study files will be password protected to ensure patient confidentiality and security of the database.

# **Quality Control Methods**

Dispensing of Study Drug

Pharmacy dispensing records will be reviewed by a study monitor on a monthly basis to ensure adherence with procedures for dispensing of Omegaven.

Legal and Ethics Requirements

This study is being conducted under a FDA Investigational New Drug Application. FDA guidelines must be followed. Federal regulations require all investigational studies be conducted under the auspices of an IRB, as defined in the Code of Federal Regulations,

Title 21, Part 56; and in accordance with the Declaration of Helsinki (1964) amended Edinburgh, Scotland (2000). The IRB will approve all aspects of the study, including the protocol and informed consent to be used and any modifications made to the protocol or informed consent prior to the initiation of the study. All changes to the protocol or consent form must be reviewed and approved prior to implementation, except where necessary to eliminate apparent immediate hazards to human subjects.

#### Informed Consent

The Investigator will be responsible for obtaining an Informed Consent signed by each patient or his/her legally authorized representative prior to his/her participation in the study in accordance with the Code of Federal Regulations, Title 21, Part 50.20. Informed Consent will be obtained from a patient or his/her legally authorized representative after a full explanation of the purpose of the study, the risks and discomforts involved, potential benefits, etc. have been provided by the Investigator or designee, both verbally and in writing. The original of the signed consent must be maintained in the patient's medical record. The person who signed the consent must also be given a copy of the signed consent form.

# Patient Confidentiality

Individual patient medical information obtained as a result of this study is considered confidential, and disclosure to third parties, other than those cited below, is prohibited. Patient confidentiality will be further ensured by utilizing patient identification code numbers and patient initials. Data generated as a result of this study will be available for inspection, on request by various regulatory agencies. These shall include all study-relevant documentation, including medical histories to verify eligibility, laboratory test results to verify transcription accuracy, treatment and diagnostic reports, admission/discharge summaries for hospital admissions occurring while the patient is on study, and autopsy reports (if available) for deaths occurring during or in temporal proximity to the study.

As part of the required content of the informed consent, patients must be informed that their records will be reviewed by various regulatory agencies.

# Retention of Records

The Principal Investigator and study staff will maintain a comprehensive and centralized filing system of all study related documentation which is suitable for inspection at any time by various regulatory agencies. These include:

- a. Patient files including source documentation and Informed Consent
- b. Study files, including the protocol with all amendments, copies of all regulatory documentation, and all correspondence with the FDA and IRB
- c. Pharmacy files including drug shipment, dispensing, and accountability records, and pharmacy-related correspondence

Per FDA regulations, the Primary Investigator will retain records for a period of two (2) years following discontinuation of the study.

# **Data Analysis Plan**

The study protocol is intended to evaluate the safety and efficacy of Omegaven® in the treatment of PN induced liver injury. Safety is addressed in the Data and Safety Monitoring Plan. Serum markers for efficacy will be monitored (bilirubin and liver enzymes). The specific data analysis will be evaluated by our statistician.

# **Statistical Power and Sample Considerations**

As discussed above, this study protocol is not intended to prove statistical significance.

## **Data and Safety Monitoring Plan**

Monitoring for toxicity due to Omegaven will be assessed by analyzing clinical and laboratory parameters including serum electrolytes, hematological studies, serum triglycerides, total cholesterol, essential fatty acid profiles, blood and urine glucose and liver and renal function tests. Blood samples will be taken prior to the start of therapy, and weekly thereafter until direct bilirubin <2mg/dL. Subsequent testing will be determined based on direct bilirubin values (as this is the monitoring standard of care for liver failure) and will be bimonthly or monthly. See Table 2 for additional information. Dose reduction will occur if there is evidence of hypertriglyceridemia (serum triglycerides > 200mg/dL), hyperglycemia (serum glucose >250mg/dL), or evidence of bleeding. Growth indices including weight, length/height, and head circumference will also be monitored. [name], the director of Pediatric Gastroenterology at LCH will be the Data and Safety Monitor. He will review patient data quarterly to ensure patient safety is upheld and that protocols are followed as described. The study will be halted in the event of one life threatening episode related to Omegaven® administration.

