#### **Dose Modification**

Hypertriglyceridemia:

If hypertriglyceridemia develops, defined as serum triglyceride levels > 200 mg/dL, the following will be considered prior to reducing the dose:

- a) If the level was obtained while the patient was receiving a continuous 24- hour infusion of Omegaven®, the total dose should be infused over 20 hours, and a repeat serum triglyceride level obtained prior to resuming the infusion 4 hours later.
- b) Other sources of hypertriglyceridemia should be considered and addressed (drugs, renal disease)

If necessary, if the triglycerides continue to remain high despite the aforementioned interventions, a dosage reduction of 25% will be considered.

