#### Overdose:

In the event of an overdose of Omegaven®, there is a risk of developing fat overload syndrome that may occur when the triglyceride level rises >200 mg/dL acutely as a result of too rapid a rate of infusion, or chronically at high infusion rates in associated with a change in the patient's clinical condition (e.g., renal dysfunction, sepsis). In such cases, the infusion should be stopped or, if necessary, continued at a reduced dose.

Metabolic acidosis has occurred in patients receiving Omegaven® at excessive doses without simultaneous administration of dextrose.

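### Two sections give conflicting instructions at the same trigger, serum triglycerides above 200 mg/dL: dose reduction is conditional and discretionary in one, unconditional in the other

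*Protocol*

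**What the plan says.** The Protocol's Dose Modification section defines hypertriglyceridemia as a level above 200 mg/dL and says that "the following will be considered prior to reducing the dose". Two steps follow. If the level was drawn during a continuous 24-hour infusion, "the total dose should be infused over 20 hours, and a repeat serum triglyceride level obtained prior to resuming the infusion 4 hours later". Other sources, such as drugs or renal disease, are also to be considered and addressed. Only then, where necessary, "if the triglycerides continue to remain high despite the aforementioned interventions, a dosage reduction of 25% will be considered".

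The Adverse Event Criteria and Reporting Procedures section refers back to these rules: "Dose modifications in the event of hypertriglyceridemia, hyperglycemia and coagulopathy will occur as described above".

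The Data and Safety Monitoring Plan, which comes later, states: "Dose reduction will occur if there is evidence of hypertriglyceridemia (serum triglycerides > 200mg/dL". The same sentence covers glucose above 250 mg/dL and evidence of bleeding. It names no intermediate step, no repeat level, no size of reduction and no other section. The same section has the Data and Safety Monitor "review patient data quarterly to ensure patient safety is upheld and that protocols are followed as described".

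**The concern.** The trigger is identical in both places, but the response differs in sequence and in obligation. This is a bedside safety rule, and a statistical analysis plan cannot repair it.

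Triglycerides are drawn at baseline and at every later scheduled visit in the laboratory monitoring table, so the trigger is checked routinely. Staff who follow Dose Modification and staff who follow the monitoring plan could handle the same result differently, each with support in the text. A reviewer asked whether the protocol was followed would have two standards to check against. The effect of Omegaven on serum triglyceride is one of the four specific aims, so inconsistent handling could also carry over into the values the study reports.

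**Working it through.** There is no sample size, power or event count to reproduce. The check is a side-by-side reading of each passage that gives an action for raised triglycerides.

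| Feature | Dose Modification | Data and Safety Monitoring Plan |
|---|---|---|
| Trigger | above 200 mg/dL | above 200 mg/dL |
| Steps before reduction | infusion time changed and level repeated (if on 24 hours); other causes addressed | none |
| Level must stay high | yes | not stated |
| Obligation to reduce | to be considered | to occur |
| Size of reduction | 25% | not stated |
| Reference to the other passage | none | none |

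**Level above 200 mg/dL on a 24-hour infusion, falling after the infusion time is changed.** Dose Modification calls for no reduction, because its condition of persistence is not met. The monitoring plan requires one. The two cannot both be followed.

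**Level that stays high after the steps.** Dose Modification leaves a 25% reduction to judgment. The monitoring plan makes a reduction mandatory, of unstated size. A clinician who reduces satisfies both sections; one who decides against it satisfies only the first.

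**Level above 200 mg/dL on a shorter infusion** (the administration section allows 12 to 24 hours). The infusion-time step does not apply, but other causes still come first under Dose Modification and not under the monitoring plan.

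The infusion-time step keeps the total daily dose. At the goal dose of 1 g/kg/day, the hourly rate goes from 1/24 = 0.042 to 1/20 = 0.050 g/kg/h, a ratio of 24/20 = 1.20. So the first step under one section leaves the daily dose unchanged, while the other section requires less drug. The gap between the two daily doses cannot be computed, because the monitoring plan gives no size.

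The choice of verb carries meaning in this protocol. For glucose above 250 mg/dL, the Hyperglycemia rule says "A minimum dosage reduction of 25% will occur". The monitoring sentence is therefore as firm as the glucose rule it covers, but firmer than the triglyceride rule. Nothing in it tells the reader that the triglyceride rule is softer.

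The general instruction to halt treatment for adverse events does not settle the matter. It applies to moderate or severe events, and the table of possible adverse events lists hypertriglyceridemia as Grade I (mild).

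**The case against.** The strongest reply is that the protocol already shows which passage controls. The detailed rule sits under the heading for dose modification, and the adverse event section refers back to it. The monitoring sentence cannot be carried out alone, since it gives no size, sequence or follow-up, so it reads as a summary. There is further support for that reading: the same sentence reduces bleeding to a dose reduction, whereas the Coagulopathy rule has other sources considered and then Omegaven reduced or halted. The sentence seems to compress two of its three rules.

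Most of this stands, and the summary reading is plausible. It does not remove the conflict. The back-reference favours Dose Modification but does not withdraw a later, unconditional statement in the section on safety monitoring. A summary that changes what must be done, and does not name its source, still has to be corrected.

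A reader might go further in three ways that the documents do not support.

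- The Overdose section also mentions levels above 200 mg/dL and says "the infusion should be stopped or, if necessary, continued at a reduced dose", which can look like a third rule for the same event. Its subject is fat overload from too rapid an infusion, or from high rates with a change in clinical condition. It is a different situation, though the shared figure makes a clear separation desirable.
- A reader might infer that the monitor would record deviations for children managed under Dose Modification. The monitor's remit is the whole protocol, which includes that section, and nothing says that the monitoring plan is used alone.
- A reader might see the secondary outcome's cut-off of 400 mg/dL as part of the conflict. It defines an outcome and is not a dosing trigger.

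**Conclusion.** The contradiction is real. At triglycerides above 200 mg/dL, Dose Modification makes a reduction conditional on persistence and discretionary, and the Data and Safety Monitoring Plan makes it unconditional. The conflict is sharpest for a child whose level falls after the infusion time is changed, where no action satisfies both sections. This conclusion rests on the wording alone, with no assumed figures.

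Its weight is modest. The protocol leans towards one passage through its back-reference, and the correction is short. It should still be made, because the matter is a safety rule for children on an investigational product.

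It may be tempting to state how far the doses diverge or how many of the planned 20 to 25 children would be affected. The documents support neither. The first would need a reduction size borrowed from Dose Modification and a single infusion scenario; the second would need a frequency of levels above 200 mg/dL that the protocol does not give.

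**What to change.** Reconcile the Dose Modification section, the adverse event section that refers to it, and the Data and Safety Monitoring Plan into one rule for triglycerides above 200 mg/dL. State it once and have the other passages cite it. The rule should make clear whether steps precede a reduction, whether persistence is required, whether the reduction is mandatory, and its size. Which rule is right is for the investigators; none is proposed here.

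In the same amendment, check that the monitoring plan's wording on bleeding agrees with the Coagulopathy rule, and that the Overdose wording is clearly marked as a separate situation.

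The cost is a wording amendment with IRB review. It needs no new visits, tests or data collection.
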